7.1.3 Safety Follow-up Period

The follow-up period for this protocol is 7 days (+2 days) from the last dose of the investigational product.

At the end of this period there will be a telephone call initiated by the site staff to query for SAEs, AEs, and concomitant treatments. All AEs and SAEs that are not resolved at the time of this contact will be followed to closure (see Section 8.1).

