7.1.4 Additional Care of Subjects After the Study

Subjects who have completed the study at Visit 6 may be evaluated for eligibility to enter a long-term safety study of SHP465.

The subject's primary care physician will be responsible for determining the appropriate and available treatment options upon study completion for subjects who did not enroll into the long-term safety study of SHP465. However, to maintain the integrity of the study, subjects will not be unblinded to treatment assignment at the end of their participation in the study.

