8 ADVERSE AND SERIOUS ADVERSE EVENTS ASSESSMENT

8.1 Definition of Adverse Events, Period of Observation, Recording of Adverse Events

An AE is any untoward medical occurrence in a clinical investigation subject administered a pharmaceutical product and that does not necessarily have a causal relationship with this treatment. An AE can therefore be any unfavorable and unintended sign (including an abnormal laboratory finding), symptom, or disease temporally associated with the use of a medicinal (investigational) product, whether or not related to the medicinal (investigational) product (ICH Guidance E2A 1995).

All AEs are collected from the time the informed consent is signed until the defined follow-up period stated in Section 7.1.3. This includes events occurring during the screening phase of the study, regardless of whether or not investigational product is administered. Where possible, a diagnosis rather than a list of symptoms should be recorded. If a diagnosis has not been made, then each symptom should be listed individually. All AEs should be captured on the appropriate AE pages in the CRF and in source documents. In addition to untoward AEs, unexpected benefits outside the investigational product indication should also be captured on the AE CRF.

All AEs must be followed to closure (the subject's health has returned to his/her baseline status or all variables have returned to normal), regardless of whether the subject is still participating in the study. Closure indicates that an outcome is reached, stabilization achieved (the investigator does not expect any further improvement or worsening of the event), or the event is otherwise explained. When appropriate, medical tests and examinations are performed so that resolution of event(s) can be documented.

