9.10 Safety Analyses

The safety data will be analyzed on the safety set. Safety endpoints include the occurrence of TEAEs, vital signs (systolic and diastolic blood pressure, pulse), BMI and weight, ECG results, clinical laboratory test results, and responses to CSHQ and C-SSRS.

Exposure to investigational product will be summarized.

Adverse events will be coded using the agreed upon version of the Medical Dictionary for Regulatory Activities. Treatment-emergent adverse events are defined as AEs that start or deteriorate on or after the date of the first dose of investigational product and no later than 3 days following the last dose of investigational product in the double-blind phase.

The number of events, incidence, and percentage of TEAEs will be calculated overall, by SOC, by preferred term, and by treatment group. Treatment-emergent adverse events will be further summarized by severity and relationship to investigational product. Adverse events related to investigational product, AEs leading to withdrawal, SAEs, and deaths will be similarly summarized/listed.

Vital signs (systolic and diastolic blood pressure, and pulse), weight, height, and BMI including potentially clinically important vital signs will be summarized by treatment and visit using the appropriate descriptive statistics.

The ECG results including potentially clinically important results will be summarized by treatment and visit.

Clinical laboratory test results will be descriptively presented by treatment group for each visit. Shifts of clinical laboratory abnormality from baseline to Visit 6/ET will be presented. Number and percent of subjects with potentially clinically important laboratory values will be presented by treatment group.

The PSQ results will be summarized by treatment and visit. Continuous variables, e.g., time to go to sleep and time spent awake, will be summarized using number of observations, mean and standard deviation, median, and minimum and maximum values. Categorical values, e.g., quality of sleep, will be summarized using number of observations and percentages. Detailed analyses of the PSQ will be described in the SAP.

The CSHQ results will be summarized by treatment and visit using appropriate descriptive statistics. Detailed analyses of the CSHQ will be described in the SAP.

The C-SSRS results will be summarized and listings of the C-SSRS data will be provided for subjects with a positive response.

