12.1 Adverse Events

Adverse events will be coded using Version 18.0 of Medical Dictionary for Regulatory Activities (MedDRA).

An AE (classified by preferred term) that occurs during the Treatment period will be considered a TEAE if it has a start date on or after the first dose of double-blind investigational product or if it has a start date before the date of the first dose of double-blind investigational product, but increases in severity on or after the date of the first dose of double-blind investigational product. An AE that occurs after more than 3 days of the last dose of double-blind investigational product will not be counted as a TEAE. If more than 1 AE with the same preferred term is reported before the date of the first dose of double-blind investigational product, then the AE with the greatest severity will be used as the benchmark for comparison to the AEs occurring during the Treatment period under the preferred term.

An overall summary of the number of subjects with TEAEs in each treatment group will be presented, including the number and percentage of subjects with any TEAEs, serious TEAEs, TEAEs related to investigational product, TEAEs leading to drug withdrawal, severe TEAEs and serious TEAEs leading to death.

The number and percentage of subjects reporting TEAEs in each treatment group will be tabulated by system organ class (SOC) and preferred term; by SOC, preferred term, and severity; and by SOC, preferred term, and relationship to investigational product. If more than 1 AE occurs with the same preferred term for the same subject, then the subject will be counted only once for that preferred term using the most severe and most related occurrence for the summarization by severity and by relationship to investigational product.

The incidence of common (≥ 2% of subjects in any treatment group) will be summarized by preferred term and treatment group, sorted in decreasing frequency for subjects on SHP465 6.25 mg, and then for placebo. The incidence of TEAEs, serious TEAEs, and TEAEs leading to withdrawal will be summarized by SOC, preferred term and treatment group, sorted in decreasing frequency for subjects on SHP465 6.25 mg, and then for placebo.

For the Safety Set, listings will be presented for all AEs, TEAEs related to investigational product, TEAEs leading to drug withdrawal, and serious TEAEs.

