18. CHANGES TO ANALYSES SPECIFIED IN PROTOCOL

18.1 Handling of the Unintentional Urine Drug Screen

At the end of this study, after completing the final on-treatment efficacy and safety assessments, urine drug screens were erroneously performed for one subject at last visit (Visit 6) and 9 subjects who were rolled over to the long-term safety extension study (SHP465-308). Thus, the site and vendor personnel might have been unblinded to treatment drug information of these subjects although a quick action was taken to remove and restrict access to the urine drug screen results. To assess any compromise to data integrity following the potential unblinding for the ten (10) subjects, Shire and PPD study teams performed a thorough investigation of data collected for study primary efficacy, secondary efficacy and safety analyses, including eCOA data collected on the ERT devices and data entered into the EDC.

This investigation showed no patterns of data changes or data integrity concerns which would be indicative of actions based on unblinded information. It was concluded that there was no evidence of the introduction of bias that would affect the aggregate data reported. In addition, Shire respects the value for each subject participant in the study, therefore decided to include all subjects in the final study analysis.

As a conservative measure to evaluate whether the potential unblinding modified the efficacy results due to the unintentional urine drug screen, sensitivity analyses of the primary efficacy (ADHD-RS-5 total score) and key secondary efficacy (CGI-I) analyses will be performed, in which these 10 subjects were excluded from the FAS (see Section 11.5).

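### The TEAE window runs to 3 days after the last double-blind dose and does not stop at the first extension dose of SHP465, so an event on active drug could be tabulated under placebo

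*SAP*

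**What the plan says.** **Window.** Protocol 9.10 counts as treatment-emergent any AE that starts or worsens from the first dose up to "no later than 3 days following the last dose of investigational product in the double-blind phase". SAP 12.1 gives the same limit as an exclusion: "An AE that occurs after more than 3 days of the last dose of double-blind investigational product will not be counted as a TEAE". The SAP's inclusion sentence carries a qualifier that the protocol lacks: "An AE (classified by preferred term) that occurs during the Treatment period will be considered a TEAE".

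**Attribution.** SAP 12.1 tabulates by arm: "The number and percentage of subjects reporting TEAEs in each treatment group will be tabulated by system organ class (SOC) and preferred term".

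**Collection.** Protocol 8.1 states: "All AEs are collected from the time the informed consent is signed until the defined follow-up period stated in Section 7.1.3". Section 7.1.3 sets that limit: "The follow-up period for this protocol is 7 days (+2 days) from the last dose of the investigational product". Neither section stops collection when a child enters the extension.

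**Extension.** Protocol 7.1.4 states: "Subjects who have completed the study at Visit 6 may be evaluated for eligibility to enter a long-term safety study of SHP465". SAP 18.1 shows that roll-over took place. It reports that urine drug screens were run in error on one child at Visit 6 and on "9 subjects who were rolled over to the long-term safety extension study (SHP465-308").

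No section of either document mentions the first extension dose when defining a TEAE.

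**The concern.** The window is anchored only to the last double-blind capsule. That is adequate for a child who then takes nothing. It is not adequate for a placebo child who goes on to SHP465 within the next 3 days, because the days credited to placebo then include the child's first exposure to active drug.

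Safety and tolerability make up the secondary objective (protocol 2.2.2, SAP 3.2). Protocol 1.2.1 names insomnia, decreased appetite and decreased weight among the events associated with SHP465, and SAP 12.1.1 gives these three their own tables. New events of this kind in a former placebo child would be entered in the placebo column. Placebo incidence would rise, and the contrast with SHP465 6.25 mg would tend to shrink on the events the plan watches most closely.

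**Working it through.** The plan states no figure for this point, so there is none to reproduce. The check has three parts: whether the rule permits the overlap, how long the overlap can be, and what one wrongly counted child is worth.

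**1. Does the rule permit it?** The protocol definition does, because it has no condition other than the 3 days. The SAP is less clear, and its sections point in different directions:

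- *Towards excluding events after Visit 6.* The qualifier in SAP 12.1 refers to the Treatment period, which SAP 2.1 gives as 4 weeks and SAP 6 ends at Visit 6. SAP 6 lists new post-treatment AEs separately. The by-week tables in SAP 12.1.1 stop at Visit 6.
- *Towards including them.* If the Treatment period closed at the last dose, the 3-day sentence would have almost nothing to do. SAP 12 limits other safety data to Visit 6 and to 2 days after the last dose, but exempts AE data from that limit. The duration rule in SAP 12.1.1 runs to 3 days after last dosing.

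The second reading is the stronger one. Under it, an event on day +2 could appear in the overall TEAE table and in none of the weekly ones.

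**2. Length of overlap per rolled-over child.** Inputs:

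- Treatment period of 28 days (4 weeks, protocol 3.2) plus 3 days, giving a 31-day window.
- g, the number of days from the last double-blind dose to the first SHP465-308 dose. The documents do not give it, so it is varied here.

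Overlap days = max(0, 3 − g + 1).

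| First extension dose | Overlap (days) | Share of 31 days |
|---|---|---|
| day +1 | 3 | 3/31 = 9.7% |
| day +2 | 2 | 2/31 = 6.5% |
| day +3 | 1 | 1/31 = 3.2% |
| day +4 or later | 0 | 0% |

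**3. Across the placebo arm.** With the 26 planned placebo completers (SAP 2.5), the window holds 26 × 31 = 806 person-days. The number of placebo roll-overs is also not given. In the worst case of dosing from day +1:

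- 5 roll-overs: 5 × 3 = 15 person-days, 15/806 = 1.9%
- 13 roll-overs: 13 × 3 = 39 person-days, 39/806 = 4.8%
- 26 roll-overs: 26 × 3 = 78 person-days, 78/806 = 9.7%

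The possible share is therefore 0% to 9.7%, and the documents do not say where in that range it falls.

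**4. Weight of one child.** Randomising 60 children 1:1 gives about 30 on placebo. One child wrongly counted adds 1/30 = 3.3 percentage points to a placebo incidence.

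**5. After the change.** If the window ends immediately before the first extension dose whenever that comes earlier, the overlap is 0 for every g. Children who do not roll over are unaffected.

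**The case against.** The strongest reply is that the harm depends on facts outside these documents. Protocol 7.1.4 says only that completers may be evaluated for the extension. No date is given for the first SHP465-308 dose, and no rule says whether an AE after roll-over is recorded under 309 or 308. If dosing starts on day +4 or later, nothing is misattributed. This stands, and it is why the size can only be given as a range that includes zero.

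A reader might infer from the urine screens in SAP 18.1 that extension dosing began within the window. The documents do not support that. A screen can separate the arms only while the placebo child has not yet taken SHP465, so the worry about unblinding suggests sampling before extension dosing. It fits prompt entry but does not date the first dose. The nine children are also only those screened in error, with no split by arm.

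The Treatment period qualifier can be argued to exclude events after Visit 6 altogether. For the reasons in the check this is the weaker reading, and the protocol definition has no such qualifier. The ambiguity is itself a reason to clarify the text.

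A reader might also see the same fault in the duration rule of SAP 12.1.1. That rule is worded for onset while on SHP465 6.25 mg, so it does not cover an event that first starts after the last placebo capsule. At most it could lengthen an existing event by up to 3 days. Aligning it is a matter of consistency.

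Finally, the effect is confined to descriptive tables, a child counts once per preferred term, and the listings for the three named events show start date and last dose date. This limits the harm, but those listings do not show when extension dosing began.

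**Conclusion.** The rule has a real gap. As written in protocol 9.10, and on the better reading of SAP 12.1, an event that begins after a placebo child has started SHP465 in the extension is a placebo TEAE if it falls within 3 days of the last double-blind dose. Whether this happens, and how often, cannot be told from the documents.

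The overlap is between 0 and 3 of 31 days (0% to 9.7%) per rolled-over child, and each wrongly counted child is worth 3.3 points of placebo incidence. These figures assume a full 28-day treatment period and about 30 placebo children. The likely direction is a narrower difference between arms in the descriptive safety tables. The primary and key secondary tests are untouched.

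Two stronger statements are not supported:

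- *That active-drug events have in fact been charged to placebo.* The dosing dates needed to show this are not given.
- *That the bias is about 1 to 16 percentage points.* A reader might get there by assuming that 25% to 90% of 26 placebo completers start extension drug within 3 days and that 5% to 20% of those have a new event: 26 × 0.25 × 0.05 = 0.33 and 26 × 0.90 × 0.20 = 4.68 children, or 1.1 and 15.6 points out of 30. Neither assumption has a basis in the documents, and the range leaves out the zero effect that they allow.

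Nor does the 2% threshold for common TEAEs add anything specific: with about 30 children per arm, any single event passes it.

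**What to change.** - In SAP 12.1 and protocol 9.10, end the TEAE window at the earlier of (a) 3 days after the last double-blind dose or (b) immediately before the first dose of SHP465-308 investigational product.
- State in SAP 12.1 that Treatment period, for AEs, means this window.
- List AEs that start after the window because of extension dosing separately, as extension-phase events.
- Apply the same cap to the end point of 3 days after last dosing in SAP 12.1.1, for consistency.

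The cost is a sentence or two of text and one additional date per rolled-over child. The documents do not show that the first SHP465-308 dose date is already in the 309 analysis data, so it would have to be brought in. The price in information is up to 3 fewer days of post-dose AE observation in children who roll over.

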The key secondary efficacy measurement will also be analyzed using the proportion of subjects with an "improved" CGI-I measurement at Visit 6/ET (Week 4/ET). In this approach, the CGI-I categories will be dichotomized into 2 categories, "very much improved" and "much improved" classified as "improved" and all other assessed categories grouped together as "not improved". If missing data exist at the Visit 6 (Week 4) visit, the visit will be imputed by carrying forward the last post baseline observation value. The secondary efficacy analysis for the dichotomized CGI-I will be conducted to compare SHP465 6.25 mg and placebo on the FAS for the "improved" rate using a Cochran-Mantel-Haenszel test stratified by age group and CGI-S value at baseline.

Treatment effect of SHP465 6.25 mg on primary and key secondary efficacy measures will be estimated using a similar model as the primary efficacy endpoint for each age group (6-8 years vs. 9-12 years), sex, race (white and nonwhite), and ethnicity subgroup.

Safety Analyses

Safety data will be analyzed for the safety set. Safety endpoints include the occurrence of TEAEs, systolic and diastolic blood pressure, pulse, and weight, height, BMI, ECG results, clinical laboratory test results, PSQ, CSHQ, and C-SSRS Exposure to investigational product will be summarized.

Adverse events will be coded using the agreed upon version of the Medical Dictionary for Regulatory Activities (MedDRA). Treatment emergent AEs will be summarized. The number and percent of subjects with TEAEs will be calculated for each system organ class, by preferred term, and by treatment. The severity of the TEAEs, the relationship to the investigational product, TEAEs causing study discontinuation, and serious AEs will also be presented.

Vital signs (systolic and diastolic blood pressure, and pulse), weight, height, BMI, and ECG results including potentially clinically important results will be summarized by treatment and visit.

Clinical laboratory test results will be descriptively presented by treatment group for each visit. Shifts of clinical laboratory abnormality from baseline to Visit 6/ET will be presented. Number and percent of subjects with potentially clinically important laboratory values will be presented by treatment group.

The PSQ and CSHQ results will be summarized by treatment and visit.

The C-SSRS results will be summarized and listings of the C-SSRS data will be provided for subjects with a positive response.

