8.2.4 Serious Adverse Event Collection Time Frame

All SAEs (regardless of relationship to study) are collected from the time the subject signs the informed consent until the defined follow-up period stated in Section 7.1.3, and must be reported to the Shire Pharmacovigilance Department and the CRO/Shire Medical Monitor within 24 hours of the first awareness of the event.

In addition, any SAE(s) considered "related" to the investigational product and discovered by the investigator at any interval after the study has completed must be reported to the Shire Pharmacovigilance Department within 24 hours of the first awareness of the event.

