8.2.5 Serious Adverse Event Onset and Resolution Dates

The onset date of the SAE is defined as the date the event meets serious criteria. The resolution date is the date the event no longer meets serious criteria, the date the symptoms resolve, or the event is considered chronic. In the case of hospitalizations, the hospital admission and discharge dates are considered the onset and resolution dates, respectively.

In addition, any signs or symptoms reported by the subject after signing the informed consent form, or leading up to the onset date of the SAE, or following the resolution date of the SAE, must be recorded as an AE, if appropriate.

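### SAP 12.1 tabulates only serious TEAEs, so SAEs starting more than 3 days after last dose are collected but have no specified count by arm

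*SAP*

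**What the plan says.** **Collection.** Protocol 8.2.4: "All SAEs (regardless of relationship to study) are collected from the time the subject signs the informed consent until the defined follow-up period" set out in Protocol 7.1.3. That section fixes the length: "The follow-up period for this protocol is 7 days (+2 days) from the last dose of the investigational product".

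**Reporting promised by the protocol.** Protocol 9.10 defines a TEAE as ending 3 days after last dose. Later in the section it drops the treatment-emergent qualifier: "Adverse events related to investigational product, AEs leading to withdrawal, SAEs, and deaths will be similarly summarized/listed". The synopsis separates the two terms within one sentence: "TEAEs causing study discontinuation, and serious AEs will also be presented".

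**Reporting planned by the SAP.** SAP 12.1 keeps the protocol's cut-off: "An AE that occurs after more than 3 days of the last dose of double-blind investigational product will not be counted as a TEAE". It then specifies these serious-event outputs:
- an overall summary, with rows for serious TEAEs and for serious TEAEs that led to death;
- a table by SOC and preferred term: "The incidence of TEAEs, serious TEAEs, and TEAEs leading to withdrawal will be summarized by SOC, preferred term and treatment group";
- a dedicated listing of serious TEAEs.

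SAP 12.1 also lists all AEs for the Safety Set, and SAP 6 lists new post-treatment AEs. SAP 18, which records changes from the protocol's analyses, covers only the unintended urine drug screens.

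**Dating.** Protocol 8.2.5: "The onset date of the SAE is defined as the date the event meets serious criteria". SAP 12.1 assigns TEAE status from the AE's start date and does not refer to the SAE onset date.

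**The concern.** The window in which SAEs are collected is longer than the window in which the SAP counts them. Following SAP 12.1 as written can give by-arm SAE and death counts below the number collected. A reader of the SAE table would have no sign that the count stops at day 3 and would have to search the general AE listings for later events.

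SAEs and deaths are few and are normally reported in full, whatever their timing relative to dosing. In an arm of about 30 children, one event more or less is visible in the reported rate. The stake is complete safety reporting. Efficacy results, the type I error rate and power are not involved.

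**Working it through.** The plan states no figure for this point, so there is none to reproduce. The check compares windows and then traces cases through the rules.

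**Inputs**
- Treatment period: 28 days (schedule of assessments, Visit 6).
- Follow-up after last dose: 7 days, up to 9 with the +2 allowance (Protocol 7.1.3).
- TEAE cut-off: last dose + 3 days (Protocol 9.10, SAP 12.1).
- Randomised: about 60 at 1:1, so about 30 per arm (Protocol 9.7).

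**Length of the uncounted span** (follow-up days minus TEAE days)
- Call at 7 days: 7 − 3 = 4 days (days 4-7).
- Call at 9 days: 9 − 3 = 6 days (days 4-9).

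**Share of treatment plus follow-up time**
- 4 / (28 + 7) = 4/35 = 11%.
- 6 / (28 + 9) = 6/37 = 16%.

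**Share of follow-up time alone**
- 4/7 = 57% and 6/9 = 67%.

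All of these are shares of time. The documents give no SAE rate, so an expected number of affected events cannot be computed.

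**Weight of one event**: 1/30 = 3.3 percentage points. This holds for any single event in an arm of that size.

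**Cases traced through the rules**
1. *SAE starts on day 2 after last dose.* Collected, a TEAE, counted in the serious outputs.
2. *SAE starts on day 5.* Collected, not a TEAE. Absent from the overall summary, the SOC/preferred term table and the serious listing. Present in the all-AE and post-treatment AE listings.
3. *Event starts on day 5 and is fatal.* As case 2, and absent from the death row.
4. *Event is serious by day 3; the child dies on day 6.* Counted. The death row depends on the event being a TEAE, and Protocol 8.2.6 records the date of death as the resolution date, not the onset.
5. *Event starts on drug and becomes serious on day 5.* Undetermined. Under Protocol 8.2.5 the SAE onset is day 5 (for a hospitalisation, the admission date), and earlier symptoms are recorded as an AE where appropriate. Protocol 8.1.1 also records a change in severity as a new event. If the SAP's start date means the onset of the underlying AE, this is a serious TEAE. If it means the SAE onset, the serious event drops out and at most a non-serious TEAE remains.

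**The case against.** **The protocol does not firmly promise a table.** Protocol 9.10 allows these events to be summarised or listed, and the synopsis says only that serious AEs will be presented. A listing could satisfy both. The adverb in 9.10 (similarly) could also be read as carrying the TEAE basis forward, since the same sentence names related AEs and AEs leading to withdrawal without the qualifier. This has force: a reader might infer that the SAP breaks a commitment to tabulate, and the text does not go that far. What stands is that the SAP's own dedicated serious listing is also limited to TEAEs. No specified output is therefore a complete SAE or death listing or count.

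**The cut-off is the protocol's own.** True, and it need not change. The gap comes from using it to limit SAEs and deaths.

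**Nothing is lost.** Correct. The late events are in two listings, SAEs are still reported within 24 hours, and a data monitoring committee reviews safety. Table specifications are in a separate document (SAP 1 and 21), so the claim is limited to what the SAP text specifies.

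**Stronger readings that the documents do not support**
- *All deaths on days 4-9 go uncounted.* Case 4 shows otherwise.
- *An event that turns serious late necessarily leaves the tables.* The SAP is silent on the deciding date, so it may or may not.
- *More than half of the SAEs could be missed.* The 57%-67% is a share of follow-up days, not of events.
- *Children stopped for a worsening event are especially affected.* Nothing in the documents shows this, and SAP 12.1 tabulates TEAEs leading to withdrawal by arm.

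**Conclusion.** The point holds as a gap in safety reporting. SAEs starting on days 4-7 (up to day 9) after last dose, and deaths from events starting then, are collected but fall outside all three serious-event outputs in SAP 12.1. They have no specified count by arm, and SAP 18 does not record the restriction. Separately, the SAP leaves open whether an event that starts on drug and becomes serious on day 4 or later counts as a serious TEAE.

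The uncounted span is 4-6 days, or 11%-16% of treatment plus follow-up time. That assumes 28 days of treatment and a follow-up call between day 7 and day 9; a child who stops early has fewer treatment days, so a larger share. That few events will be affected is a judgement from the small trial and short treatment, not a computed figure. The change is worth making because it is cheap and concerns the most serious events in a paediatric trial.

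**What to change.** In SAP 12.1:
- Add a by-arm table row and a listing of all SAEs and all deaths from first dose to the end of the Protocol 7.1.3 follow-up, or to the first SHP465 dose in the long-term extension study if that is earlier.
- Keep serious TEAEs as a flagged subset, so that the row already planned is unchanged.
- List SAEs between consent and first dose separately.
- State that the TEAE flag for an SAE uses the onset date of the underlying AE, not the date on which it met serious criteria.
- Record the change in SAP 18. If the sponsor prefers to keep the restriction, declaring it there is the minimum.

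The cost is some SAP wording, one row or table and one listing, all from data already collected. The downside is that a few off-drug events enter the all-SAE count; the flag keeps them distinguishable.
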